2.4 SAMPLE SIZE DETERMINATION

Estimation of sample size to achieve a desired power depends on the number and nature of the hypothesis testing paradigm and assumptions about the magnitude of the underlying effects. In this trial, hypothesis testing will proceed in the following order. First MWT and CGI will be examined for statistical significance in the full sample including both NT1 and NT2 patients for the 9 g dose. If significant, NCA for the same dose will be tested in NT1 patients. If the first test fails, the data for this dose is not able to reject the null hypothesis of equality to placebo. If the first test is significant, but the second fails, the dose has been demonstrated to be superior to placebo for EDS treatment, but not for cataplexy. If both tests are statistically significant, the dose has been shown to be effective for both EDS and cataplexy treatment. The same sequence of testing will be followed for the 7.5 g dose. If both tests are statistically significant, the dose has been shown to be effective for both EDS and cataplexy treatment and the same sequence of testing will then be followed for the 6 g dose. Each dose will be tested at the two-sided alpha level of 0.05.

2.5 RANDOMIZATION AND BLINDING

2.5.1 INTERIM ANALYSIS AND UNBLINDING.

There are no planned interim analyses. Other than individuals unblinded for safety issues, the data will remain blinded until after the database is locked.

2.5.2 DATA AND SAFETY MONITORING BOARD (DSMB)

An independent DSMB will be appointed to review and assess study conduct and safety for the duration of the clinical trial.

2.6 STUDY ENDPOINTS

The endpoints for evaluating EDS in both NT1 and NT2 narcolepsy patients are the Maintenance of Wakefulness Test (MWT), Clinician Global Impression (CGI) and secondarily the Epworth Sleepiness Scale (ESS).

The endpoint for evaluating cataplexy in NT1 narcolepsy patients is the mean number of daily cataplexy attacks (NCA) as determined from the Sleep and Symptom Daily Diary during the Period

2.6.1 PRIMARY ENDPOINTS FOR EFFICACY

2.6.1.1 PRIMARY ENDPOINTS FOR EDS

The co-primary endpoints for evaluating EDS in both NT1 and NT2 narcolepsy patients is mean sleep latency on the Maintenance of Wakefulness Test and the Clinician Global Impression for sleepiness. The MWT is the mean latency across 5 naps, averaged over the test day and the CGI is the clinician's global impression of improvement in daytime sleepiness.

2.6.1.2 PRIMARY ENDPOINT FOR CATAPLEXY

The primary endpoint for evaluating cataplexy is the number of cataplexy attacks, which will be evaluated only on the narcolepsy NT1 subpopulation. The NCA is the mean number of cataplexy events recorded on the Sleep and Symptom Daily Diary (SSDD) during the Period. Because of concern about the variability of this measure, a minimum number of diary entries of 3 per week is required for the average to be considered an observation. If

the number of days with entries is less than three, the mean NCA for that week will be considered missing.

2.6.2 SECONDARY/EXPLORATORY ENDPOINTS

The secondary/exploratory efficacy endpoints are

[REDACTED]

2.6.3 ENDPOINTS FOR SAFETY

Safety will be evaluated based on reports of adverse events either spontaneously reported or observed in clinical laboratory analyses. All adverse events and all serious adverse events will be tabulated by system organ class and preferred term.

3. ANALYSIS SETS

The intent to treat and per protocol populations form the bases for the evaluation of efficacy. The safety population forms the basis for the evaluation of safety.

3.1 THE INTENT TO TREAT (ITT) POPULATION

The ITT population includes all randomized subjects with at least one efficacy measurement after receiving the 6 g dose (whether FT218 or placebo.) A valid diary measurement is defined to include at least 3 days of entries per week. Diary measurements with fewer days will be treated as missing, and if there are no other measurements will not

qualify the subject for the ITT population. Patients will be assigned to treatment groups in the analysis as randomized.

3.2 THE PER PROTOCOL (PP) POPULATION

The PP population includes all subjects in the ITT population reduced by those who failed to follow the protocol with respect to protocol deviations. These are inclusion or exclusion criteria not satisfied (protocol chapter 8, sub-sections 8.3.2 and 8.3.3), deviations related to study drug administration, deviations to the schedule of visits and procedures (protocol chapter 9) or deviations related to concomitant medications not permitted (protocol chapter 8, sub-section 8.4.8.1). Subjects will be assigned to treatment groups as randomized.

3.3 THE SAFETY (S) POPULATION

The S population includes all subjects that receive at least one dose of study medication. Subjects will be assigned to treatment group based on the treatment actually administered.

4. DESCRIPTION OF STATISTICAL ANALYSIS

The formal statistical analysis and specific dose/placebo contrasts will be based on a mixed-effects repeated measures (MMRM) means model or a corresponding generalized mixed-effects model (GLIMMIX) in case of categorical data. Descriptive statistics characterizing the study population and the observed outcomes will be produced.

4.1 GENERAL CONSIDERATIONS

All statistical tests will be performed using a two-tailed 5% overall significance level, unless otherwise specified. The null hypothesis for all tests is that FT218 and placebo have equal means. All sample mean outcome differences between the study treatments/doses will be reported with 95% confidence intervals. The *p*-value will be presented for each statistical test; if the value is less than 0.05, 0.01 or 0.001, the result will be highlighted by the respective annotation *, ** or ***.

Descriptive statistics will be provided by dose group and as a summary across all dose groups.

4.1.1 STANDARD DESCRIPTIVE STATISTICS

CONTINUOUS VARIABLES

Standard descriptive statistics will be reported for continuous variables including number of non-missing observations, mean, median, standard deviation, 95% confidence interval for the mean, median, inter-quartile range, minimum, and maximum value.

CATEGORICAL VARIABLES

Standard descriptive statistics will be provided for categorical variables in contingency tables with cell frequencies and percentages for the number of non-missing observations. Entries will include total number, number missing, number available, number for each category, and the corresponding percentage of the total number of values available for each category.

4.1.2 DEFINITION OF STUDY VISITS

Study visits are identified by the week of the visit.

At Week -1 (Baseline) a full baseline evaluation will take place. Thereafter with full efficacy assessments occurring at week 3 for the 6 g dose, week 8 for the 7.5 g dose and week 13 for the 9 g dose. Visits with partial efficacy assessments (MWT and PSG are excluded) occur following the first two weeks on the 7.5 g dose (week 6 day 1) and following the first two weeks on the 9 g (week 11 day 1).

4.1.3 ANALYSIS ASSESSMENT WINDOWS

Comparison between specific doses and placebo utilize measurements from comparable periods in the study. Thus, there will be 3 sets of placebo measurements; one corresponding to the 6 g dose (weeks 2 and 3), one corresponding to the 7.5 g dose (weeks 4 through 8) and one corresponding to the 9 g dose (weeks 9 through 13.)

4.1.4 TREATMENT START/STOP DATES

Treatment in the FT218 arm will begin on Day 1, Week 1 at 4.5 g dose. The dose will be increased to 6 g on Day 1, Week 2 and to 7.5 g on Day 1, Week 4. The dose will increase to 9 g on Day 1, Week 9 and continue at that dosage until Day 7, Week 13.

4.1.5 TABLES, LISTINGS AND FIGURE PRESENTATION

The treatment groups will be displayed in the tables, listings and figures as

Group 1:	9 g	(Period 3c (i) and 3c (ii), weeks 9-13)
Group 2:	Placebo	(Period 3c (i) and 3c (ii), weeks 9-13)
Group 3:	7.5 g	(Period 3b (i) and 3b (ii), weeks 4-8)
Group 4:	Placebo	(Period 3b (i) and 3b (ii), weeks 4-8)
Group 5:	6 g	(Period 3a, weeks 2-3)
Group 6:	Placebo	(Period 3a, weeks 2-3)

The listings will display all of the data contained in the eCRF. The listings will be ordered by the treatment groups shown above.

Summaries of continuous variables will use the following descriptive statistics: n, mean, standard deviation, 95% confidence interval of the mean, median, interquartile range, minimum and maximum.

The number of decimal places to be displayed for each statistic will be as follows:

- Mean, 95% confidence intervals, median and interquartile range: one more decimal place than data.
- Standard deviation: two more decimal places than the data.
- Minimum and maximum: same number of decimal places as the data.
- P-value: 3 decimal places, if less than 0.001 then display as “<0.001”.

Categorical variables will be presented as frequency counts and percentages. Percentages will be displayed to one decimal place throughout.

All dates will be displayed in the format DDMMYYYY

Calculations using dates will follow these conventions:

The relative study day of the event (DAY) is calculated as the difference between the date of the event of interest (EVENT DAY) and the date of first dose of study medication (FIRST DOSE), i.e.

$$\text{DAY} = \text{EVENT DATE} - \text{FIRST DOSE} + 1 \quad \text{for EVENT DATE} \geq \text{FIRST DOSE}$$

$$\text{DAY} = \text{EVENT DATE} - \text{FIRST DOSE} \quad \text{for EVENT DATE} < \text{FIRST DOSE}$$

Durations will be calculated by: $\text{DURATION} = (\text{STOP DATE} - \text{START DATE}) + 1$

4.1.6 USE OF ANALYSIS SETS

For the primary statistical analyses of efficacy endpoints, the ITT will be used; a supportive analysis will be carried out on the PP population unless it is essentially the same as the ITT population, if the difference in sample sizes is less than 10%. All safety endpoints analysis will be conducted on the Safety population.

4.1.7 ANALYSIS OF SUBGROUPS

The primary efficacy analyses for EDS will be performed on the full ITT population. The primary efficacy analyses for cataplexy will be performed on the NT1 subgroup of the ITT population.

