7.1 Primary Objective

The primary objective of the study is:

- To compare the efficacy of 6.0, 7.5, and 9.0 g of FT218 to placebo in treating EDS in both NT1 and NT2 subjects as measured by mean sleep latency on the Maintenance of Wakefulness Test (MWT) and by the Clinical Global Impression (CGI) rating of sleepiness
- To compare the efficacy of 6.0, 7.5, and 9.0 g of FT218 to placebo in treating cataplexy in NT1 subjects as measured by the number of cataplexy attacks (NCA) determined from the cataplexy frequency item in the Sleep and Symptom Daily Diary

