2.1.1 PRIMARY OBJECTIVES

- To compare the efficacy of 6.0, 7.5, and 9.0 g of FT218 to placebo in treating EDS in both NT1 and NT2 subjects as measured by mean sleep latency on the Maintenance of Wakefulness Test (MWT) and by the Clinical Global Impression (CGI) rating of sleepiness
- To compare the efficacy of 6.0, 7.5, and 9.0 g of FT218 to placebo in treating cataplexy in NT1 subjects as measured by the number of cataplexy attacks (NCA) determined from the cataplexy frequency item in the Sleep and Symptom Daily Diary

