4.6 EFFICACY ANALYSIS

Two patient populations, one with both narcolepsy symptoms (EDS and cataplexy) and one with only EDS will be studied in a single parallel groups, dose-escalation design. The treatments are placebo and increasing doses of the test drug, FT218. Two primary outcome measures, MWT and CGI quantify the treatment effect on EDS and the NCA is the primary

outcome measure for cataplexy. All ITT or PP subjects will be included in the evaluation of EDS and all ITT or PP subjects with both conditions will be used in the evaluation of cataplexy.

Subject demographics and baseline characteristics will be tabulated for all randomized subjects. The baseline comparability of treatment groups with respect to subject demographics and baseline characteristics will be described, but formal statistical tests will not be performed.

4.6.1: PRIMARY ANALYSIS:

A mixed effect repeated measures (MMRM) means model will be used to analyze change from baseline for MWT and cataplexy. Each model will include treatment, time (at which the measurement was taken), treatment-by-time interaction, site and baseline score as fixed effects and subjects as random effects. In fitting the model, time will range over the entire period of observations.

For CGI, a GLIMMIX model for binomial data with logit link will be used instead of a MMRM to analyze the categorized CGI response, i.e., proportion of patients who were very much or much improved. The observed values for the categorized response (very much or much improved versus other category) will be used as responses in the model. Each model will include treatment, time (at which the measurement was taken), treatment-by-time interaction and site as fixed effects and subjects as random effects. In fitting the model, time will range over the entire period of observations. The odds ratio, 95% confidence intervals for the odds ratio and p-value will be provided.

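### The EDS objective names both narcolepsy types, but the readable plan tests EDS only in the pooled sample, with no type term in the models and no estimate by type

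*SAP*

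**What the plan says.** Protocol 7.1 sets the EDS objective as a comparison of each dose "to placebo in treating EDS in both NT1 and NT2 subjects"; SAP 2.1.1 repeats it. The test that serves this objective is pooled. SAP 2.4 says "First MWT and CGI will be examined for statistical significance in the full sample including both NT1 and NT2 patients for the 9 g dose", and SAP 4.1.7 says "The primary efficacy analyses for EDS will be performed on the full ITT population".

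SAP 4.6.1 lists the model terms. For MWT they are treatment and time, followed by "treatment-by-time interaction, site and baseline score as fixed effects and subjects as random effects". For CGI they are treatment and time, followed by "treatment-by-time interaction and site as fixed effects and subjects as random effects". Neither list includes narcolepsy type, and the CGI list has no subject-level baseline covariate. Protocol 11.9.1.1 gives the same lists, with a redaction after the MWT and cataplexy terms.

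In the readable subgroup text, type has one use: "The primary efficacy analyses for cataplexy will be performed on the NT1 subgroup of the ITT population". The decision rule in SAP 2.4 puts no limit by type on an EDS conclusion. If EDS succeeds and cataplexy fails, "the dose has been demonstrated to be superior to placebo for EDS treatment, but not for cataplexy".

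**The concern.** A significant pooled test supports an effect averaged over whatever mix of types is enrolled. It does not separate a similar effect in both types from a large effect in NT1 and little in NT2. No readable step of the analysis tests or displays the word *both* in the objective.

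The documents give reasons to look. Protocol 6.1.2 attributes NT1 to loss of hypocretin cells and defines NT2 by hypocretin above 110 pg/mL. Protocol 8.3.2 requires NT1 subjects to average 8 cataplexy attacks per week before randomization. Protocol 6.5 presents the sample as largely representative of the wider NT1 and NT2 population and rests generalizability on that. Type is confirmed for every subject at Visit 1 (Protocol 9.1.1), so no new data are needed.

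At stake are the interpretation of the EDS result for NT2 and some efficiency from leaving out a known baseline factor. The type I error of the pooled test is not in question.

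**Working it through.** **Inputs.** Two-sided alpha of 0.05 (SAP 2.4) and 1:1 allocation (Protocol 8.4.9, alert card). Sample size, design power, effect size, SD and the NT1:NT2 mix are not in the public text, so no figure of the plan can be reproduced. Everything below is illustration under stated assumptions, by normal approximation, with equal variance and 1:1 allocation within each type.

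**Chance that an NT1-only effect passes the pooled test.** Let the pooled design have power P for a common effect d. Then d/SE = 1.960 + z(P). If the effect is d in NT1 (share f) and zero in NT2, the pooled effect is f × d and

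power = Φ(f × (1.960 + z(P)) − 1.960).

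For P = 0.90, d/SE = 1.960 + 1.2815 = 3.2415.

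| NT1 share f | 3.2415f − 1.960 | One endpoint | MWT and CGI, if independent |
|---|---|---|---|
| 0.50 | −0.339 | 37% | 13% |
| 0.60 | −0.015 | 49% | 24% |
| 0.75 | 0.471 | 68% | 46% |
| 0.80 | 0.633 | 74% | 54% |
| 0.90 | 0.957 | 83% | 69% |

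The last column is the square of the unrounded single-endpoint probability, taking 90% power for each endpoint. If the endpoints were fully correlated, the joint probability would equal the single-endpoint column. The truth lies between, if the endpoints are positively correlated. For one endpoint over f = 0.50 to 0.90, the range is 29% to 71% at 80% design power and 44% to 90% at 95%.

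**What by-type estimates could show, in units of d.** With 90% pooled power, the NT2 half-width is 1.96/(√(1−f) × 3.2415) in units of d. Power in NT2 alone for the full effect d is Φ(√(1−f) × 3.2415 − 1.960). Power for a treatment-by-type difference of d is Φ(√(f(1−f)) × 3.2415 − 1.960).

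| f | NT2 half-width | Power, NT2 alone | Power, contrast |
|---|---|---|---|
| 0.50 | 0.86d | 63% | 37% |
| 0.75 | 1.21d | 37% | 29% |
| 0.90 | 1.91d | 17% | 16% |

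**The same in SD units,** assuming a total N of 160 to 260 and an NT2 share s of 20% to 40%:

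- NT2 half-width = 1.96 × 2/√(N × s). This runs from 3.92/√(260 × 0.4) = 0.38 SD to 3.92/√(160 × 0.2) = 0.69 SD.
- NT1-minus-NT2 contrast half-width = 1.96 × 2/√(N × s(1−s)). This runs from 3.92/√(260 × 0.24) = 0.50 SD to 3.92/√(160 × 0.16) = 0.77 SD.

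The SD figures apply to MWT. For the CGI odds ratio, the dilution formula is only a rough guide.

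**The case against.** The strongest reply is that the redactions sit where an answer would be. The SAP contents show a blacked-out heading after 4.1.7 and two more after 4.6.2. The randomization text (SAP 2.5, Protocol 11.2.2) and the secondary/exploratory endpoints (SAP 2.6.2) are not readable. By-type summaries or stratification by type could be there. This stands: one can say only that the public text has no by-type estimate, and nothing can be said about whether the analysis ignores a stratification factor.

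Second, the plan is coherent on its own reading. *Both* may describe who is enrolled and not two separate claims, and the pooled test answers that question validly. The types share the same EDS entry criteria, and the MWT model already adjusts for baseline MWT. The documents also state prior sodium oxybate efficacy for EDS in both types (Protocol 6.1.2.2 and 6.5). This makes a zero NT2 effect an extreme case, so the tables above are a stress test and not a forecast. It does not remove the value of showing the NT2 result for a new formulation.

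Third, a reader might infer that the trial would usually declare efficacy in both types when NT2 has none. Assuming 0.6 SD in NT1 and N = 200, MWT power is 92%, 84% and 72% with 20%, 30% and 40% NT2. But that assumption implies Φ(0.6 × √50 − 1.96) = 98.9% design power, which no readable text supports. It also counts MWT alone: with equal CGI power and independence, 72% becomes 0.72² = 52%. *Could* is supported; *usually* is not.

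**Conclusion.** The concern holds as a gap in interpretation and reporting. The readable plan pools the types for EDS, omits type from both listed models and shows no effect by type, while the objective names both. Under an assumed 90% power per endpoint and an NT1 share of 50% to 90%, an NT1-only effect would pass one endpoint 37% to 83% of the time. It would pass both 13% to 69% of the time if they are independent, with 37% to 83% as the ceiling under full correlation.

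Two further inferences fail. By-type intervals would not reliably expose such a result: the contrast half-width of 0.50 to 0.77 SD is close to or above an assumed difference of 0.6 SD, and power to detect that difference is only about 33% to 66%. Nor would requiring a favourable direction in NT2 protect the claim. A null NT2 effect would meet that rule half the time, and a true effect of 0.3 SD would fail it 6% to 20% of the time under the same N and mix.

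**What to change.** In SAP 4.6.1 and Protocol 11.9.1.1:

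- Add narcolepsy type as a fixed effect to the MWT and CGI models, and state whether type is a randomization stratum.
- Pre-specify a supportive model for each endpoint with treatment-by-type and its interaction with time.
- From that model, report the 9 g, 7.5 g and 6 g effects against placebo with 95% CIs in NT1 and in NT2, plus the treatment-by-type contrast. Label all of these descriptive, with no alpha spent and no direction rule as a condition for any claim.
- If a redacted section already provides this, a cross-reference from SAP 4.1.7 is enough.

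The cost is SAP and protocol wording and one supportive model per endpoint, settled before unblinding. It needs no patients, visits or new data. The drawback is imprecision: the NT2 estimate and the contrast will often be compatible both with no effect and with a full one, and the report should say so.

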4.2 SUBJECT DISPOSITION

The number of subjects within each dose of each analysis population will be summarized. The number of subjects entering each Period of the study will be tabulated along with number of subjects who withdraw. The timing of withdrawal and reasons for withdrawal (adverse event, lost to follow-up, withdrawal by subject, withdrawn due to physician decision, non-compliance with study drug, due to pregnancy, lack of efficacy, death, other reasons) will be summarized by treatment for each Period of the study and summarized over all Periods in the randomization stage.

4.3 DEMOGRAPHICS AND BASELINE SUBJECT CHARACTERISTICS

Subject demographics will be presented by treatment arm and for the total study. Baseline will be defined as the measurement in Period 2, prior to randomization. Initial data at screening will also be reported for all screened subjects.

Cases for which the entry criteria or other protocol requirements were violated will be identified and their baseline characteristics will be summarized.

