2.3 SCHEDULE OF EVENTS

The clinical trial design is comprised of four periods: screening, wash-out/baseline (which includes randomization), double-blind-treatment and follow-up. These are shown in Table 1. After randomization, the doses of the FT218 arm begins at 4.5 g where it remains for one week (Period 3a), then it is titrated to 6 g where it remains for two weeks (Period 3a), then to 7.5 g where it remains for five weeks (Period 3b (i) and 3b (ii)) and finally to 9 g for the final 5 weeks (Period 3c(i) and 3c(ii)).

[REDACTED]

Table 1. Schedule of Events				
Period	Week(s)	Phase of Study		Evaluations
1	Week -3 to Week 0	Week -3 Screening Visit Week -3 Day 1 Commence Sleep and Symptom Diary Week -1 D7 Overnight PSG and next day 4 Nap MWT		Full screening and enrolment evaluation Full Baseline Evaluation (D7 W-1 – PSG; D1 W0 Next day MWT)
2	Week 0***	Week 0 + Max 2 days Central Scoring Lab Results Week 0 D2 or D3 Randomization		
		FT218 Arm	Placebo Arm	
3a	Weeks 1-3	Week 1: 4.5g Week 2-3: 6.g	Placebo	Full Efficacy Assessment* Visit 4 (D7 Week 3 and D1 Week 4)
3b(i)	Weeks 4-5	7.5 g	Placebo	
3b(ii)	Weeks 6-8	7.5 g	Placebo	Partial Efficacy Assessment** done at Visit 5 (D1 Week 6) Full Efficacy Assessment* at Visit 6 (D7 Week 8 and D1 Week 9)
3c(i)	Weeks 9-10	9g	Placebo	
3c(ii)	Weeks 11-13	9 g	Placebo	Partial Efficacy Assessment** at Visit 7 (D1 Week 11) Full Efficacy Assessment* at Visit 8 (D7 Week 13 and D1 Week 14)
3c(iii)	Week 14	End of Study Visit (EOS)		
4	Week 15	Follow-up Visit		

1.* Full efficacy assessment occur on the last day of a period and extend into the following day of the next period.

2.** Partial efficacy assessment (MWT and PSG are excluded) occur following the first two weeks on the 7.5 g dose and following the first two weeks on the 9 g dose during respective periods.

3.*** Maximum of 2 day turnaround for PSG and MWT results from Central Scoring Laboratory

Table 2: Study Design

Screening and Baseline		Rand	Dose Titration			Dose Titration			Stable Dosing					EOS	FU		
					7.5g	7.5g	7.5g	7.5g	7.5g	7.5g	9.0g	9.0g	9.0g	9.0g	9.0g		
		Arm 1	4.5g	6g	6g												
		Arm 2	Placebo														
				Placebo	Placebo												
						Placebo	Placebo	Placebo	Placebo	Placebo							
											Placebo	Placebo	Placebo	Placebo	Placebo		
Visit 1	Visit 2*		Visit 3***	Visit 4*		Visit 5**	Visit 6*		Visit 7**		Visit 8*	Visit 9					

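### Does the SAP's Period 2 baseline rule leave the cataplexy endpoint without a usable baseline?

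*SAP*

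**What the plan says.** SAP 4.3, on demographics and baseline characteristics, states: "Baseline will be defined as the measurement in Period 2, prior to randomization". It is the only general baseline definition in the readable SAP; laboratory data have their own rule in SAP 4.7.

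SAP 2.6 defines NCA as the "mean number of daily cataplexy attacks (NCA) as determined from the Sleep and Symptom Daily Diary during the Period", and SAP 2.6.1.2 adds that "a minimum number of diary entries of 3 per week is required for the average to be considered an observation". SAP 4.6.1 models change from baseline for cataplexy, with the baseline score as a covariate. Under SAP 4.6.2, success on NCA at 9 g is required before 7.5 g and then 6 g can be tested.

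The timing of baseline is described in several ways:

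- SAP Table 1 gives Period 2 as Week 0, with "Week 0 D2 or D3 Randomization". The diary start, "Week -3 Day 1 Commence Sleep and Symptom Diary", is in the Period 1 row.
- The prose of SAP 2.3 names the four periods as "screening, wash-out/baseline (which includes randomization), double-blind-treatment and follow-up".
- SAP 4.1.2 says: "At Week -1 (Baseline) a full baseline evaluation will take place".
- Protocol 11.6 takes the latest measurement before randomization.
- Protocol 9.1.2 places Visit 2 (Week -1, Day 7), called the baseline visit, at the head of Period 2.

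**The concern.** For a single-visit measure such as the MWT, SAP 4.3 causes no difficulty. For a diary mean it does. Taken with Table 1, it confines the NCA baseline to the day or two of Week 0 before randomization, which falls short of the 3-entry minimum. Protocol 9.1.1 explicitly requires daily pre-treatment entries only for Period 1, so the literal count could even be zero. A subject without a baseline has no change score and would leave the NCA model.

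The other descriptions do not agree on a replacement window. They can be read as one week, three weeks or, for protocol 11.6, a single day. Because the 9 g NCA test gates both lower doses, an unnamed window looks like analyst discretion in the wrong place.

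There is also a wording difference for short weeks. SAP 2.6.1.2 sets only that week's mean to missing, while protocol 11.9.1 can be read as voiding the whole mean.

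**Working it through.** **1. The literal day count.** Inputs: randomization on Week 0 Day r, with r = 2 or 3 (SAP Table 1), and at least 3 entries per week (SAP 2.6.1.2). Days strictly before randomization number r − 1 if Period 2 starts on Week 0 Day 1, and r if it starts at Visit 2 (protocol 9.1.2). Counting the randomization day adds one.

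| Start of Period 2 | Randomization day | Randomized Day 2 | Randomized Day 3 |
|---|---|---|---|
| Week 0 Day 1 | not counted | 1 | 2 |
| Week 0 Day 1 | counted | 2 | 3 |
| Week -1 Day 7 | not counted | 2 (1 in Week 0) | 3 (2 in Week 0) |
| Week -1 Day 7 | counted | 3 (2 in Week 0) | 4 (3 in Week 0) |

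By study week, 3 entries are reached only with randomization on Day 3, that day counted, and every day completed. The arithmetic behind the concern is right.

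**2. Whether that window is what the plan means.** Four places say otherwise.

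- SAP 3.1 and protocol 11.3.1 both make 3 days of entries per week the condition for a valid diary measurement. A 1- or 2-day remnant is therefore not a measurement in the plan's own terms, and a single day cannot be the latest one under protocol 11.6.
- Protocol 9.1.2 opens Period 2 with Visit 2. There the site checks compliance with the diary already kept, which it labels screening/baseline, and confirms the NT1 weekly attack average from it.
- The protocol uses the same backward-looking pattern later. Visit 4 heads Period 3b(i) but assesses 6.0 g. Visit 6 heads Period 3c(i) but assesses 7.5 g. Visit 8 heads Period 3c(iii) but assesses 9.0 g. Each checks the diary for the preceding 3 weeks. Visit 2 fits this pattern.
- As Table 1 reads, its Period 1 row also holds the baseline PSG and MWT. Using its rows to decide which data count as baseline would move the MWT baseline out of Period 2 too, which nobody intends.

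**3. Whether the data exist.** Protocol 8.3.2 requires at least 4 diary entries in each of the 3 screening weeks before randomization. That is 4 × 3 = 12 entries at minimum, and each week passes the 3-entry rule because 4 ≥ 3. No eligible NT1 subject lacks a valid pre-randomization diary.

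**4. Size of the remaining choice.** For illustration, take the entry threshold of 8 attacks per week (8/7 per day), a stable rate, independent days, and an assumed variance-to-mean ratio φ of 1 to 3.

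- CV of one subject's baseline from d days = √(φ / (d × 8/7)). For d = 7: 35% to 61%. For d = 21: 20% to 35%.
- SD of (last 7 days minus all 21 days) = √(φ × 8/7 × (1/7 − 1/21)) = 0.33 to 0.57 per day. That is 29% to 50% of the mean, or 2.3 to 4.0 attacks per week.

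This is noise in one subject's pre-randomization covariate. With baseline in the model, the dose contrast is the same whether change or the raw count is the outcome. A noisier baseline therefore costs some precision and does not shift the comparison.

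**5. The short-week wording.** With 7 independent days and daily completion q, P(fewer than 3 entries) is 0.5%, 2.9% or 9.6% at q = 80%, 70% or 60%. If one short week voided a 3-week mean, the loss 1 − (1 − p)³ would be 1.4%, 8.4% or 26.2%. The difference matters only at poor completion. It cannot affect the baseline, where every week has at least 4 entries. Both documents already define diary validity by the week.

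**The case for a change.** The best argument for a change is that a primary, gating endpoint should have its baseline named. SAP 4.3 is the only general rule in the readable SAP, laboratory data get a rule of their own, and NCA does not. The sensible reading is also not unique, since the last screening week and all three weeks are both defensible. A sentence would settle it, and all the data are in hand.

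Part of this stands: no readable sentence states which diary days form the NCA baseline. The claimed consequences do not. Baselines will not be missing (step 3). Any window lies before randomization and applies to both arms, so it gives no bias between them. No power loss can be claimed, because the sample size is not readable. Under SAP 2.5.1 the data stay blinded until database lock, so the window can be fixed without sight of results.

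Prescribing all three weeks would not be a clear gain either. Protocol 9.1.1 starts washout at Visit 1, and protocol 6.1.2.1 notes that withdrawing REM-suppressing drugs can provoke attacks. Early screening weeks may therefore overstate the settled rate, while dropping them loses precision.

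Finally, the body of protocol 10.1.1.3 on the diary is not readable, and text beside the model description in protocol 11.9.1.1 and subsections after SAP 4.6.2 are redacted. A rule may sit there, and its absence from view is not evidence of a gap.

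**Conclusion.** The concern does not call for a change. The day count is correct, but it depends on reading a general sentence and a schedule table more literally than the plan's diary-validity rule and visit structure allow. The natural reading is the screening diary reviewed at Visit 2, and every eligible NT1 subject has three valid weeks of it.

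The residue is an unnamed choice of weeks. Under the assumptions in step 4 it moves an individual baseline by an SD of 2.3 to 4.0 attacks per week; it favours neither arm and can be settled under blind. The short-week mismatch is a wording difference of little consequence unless completion is low. This conclusion assumes that the diary entry criteria in protocol 8.3.2 are enforced and that the window is fixed before unblinding.
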